6.3.1.2 What is the combined diagnostic accuracy of any 2 ultrasound metrics?

The incremental value of using a second ultrasound metric will be analyzed by constructing separate ROC curves for combinations of any 2 ultrasound metrics.

6.3.1.3 What is the combined diagnostic accuracy of ultrasound metrics and mammography?

We will select ultrasound metrics with an AUC exceeding 0.75 in C.1.a-b, and their combined diagnostic accuracy with mammography measures (mass size, density, shape, and margins) will be analyzed in separate ROC curves.

6.3.1.4 Which cutpoints for ultrasound metrics detect malignancy with optimum sensitivity and specificity?

Best-balanced cutpoints from the highest performing ultrasound metrics in 6.3.1.1 will be derived from ROC curves, using Youden's Index. These cutpoints will be used to analyze the PPV.

6.3.2 Aim #2: Correlate ultrasound-derived stiffness, elasticity, viscosity, and anisotropy with response to treatment.

In 40 women with newly diagnosed invasive breast cancer who are scheduled to begin clinically indicated NAC, ARFI, VisR, and DDAI imaging will be performed (as described in Aim #1) at baseline, early within each chemotherapy type, and at the conclusion of each chemotherapy type over the course of treatment.

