2.1.3 Determine the combined diagnostic accuracy of ultrasound metrics and mammography.

For ultrasound outcome metrics (singly or combined) with AUC exceeding 0.75 in 2.1.1 and 2.1.2, we will determine if combining the metrics with mammography-derived mass size, density, shape, and margins improves ROC performance relative to not combining with mammography.

2.1.4 Determine which cutpoints for ultrasound metrics detect malignancy with optimum sensitivity and specificity.

Best-balanced cutpoints from the highest performing ultrasound metrics in 2.1.1 will be derived, and PPV will be calculated.

2.2 Aim #2: Quantify the ability of ultrasound-derived stiffness, elasticity, viscosity, and anisotropy to predict a positive response to treatment.

In 40 women with newly diagnosed invasive breast cancer who are scheduled to begin clinically indicated NAC, ARFI, VisR, and DDAI imaging will be performed (as described in Aim #1) immediately before beginning treatment and then over the course of treatment. The eight ARFI, VisR, and DDAI outcome metrics described in Aim #1 will be statistically correlated with clinically determined change in tumor size following NAC treatment. ARFI, VisR, and DDAI outcome metrics will also be evaluated for ability to predict positive response to NAC, with positive response determined according to the RECIST guidelines.^{1,2}

2.2.1 Determine which baseline ultrasound metric best predicts positive response to NAC.

We will statistically determine, from among all eight ultrasound outcome metrics acquired at each imaging time point, which metric best predicts positive response to treatment, with positive response determined according to the RECIST guidelines.^{1,2}

2.2.2 Determine which baseline ultrasound metric correlates most strongly with absolute reduction in tumor size.

We will correlate absolute change in tumor size (diameter and area) from baseline to end of chemotherapy type with ultrasound metric values at baseline.

2.2.3 Determine the combined ability of any 2 baseline ultrasound metrics for prediction of positive response to NAC.

We will systematically combine all possible groupings of any two ultrasound outcome metric values at baseline. We will then statistically analyze the combined ability to predict reduction in tumor size.

2.2.4 Determine if serial changes in ultrasound metrics correlate with positive response to NAC.

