6.0 STATISTICAL CONSIDERATIONS

6.1 Study Design/Study Endpoints

For Aims #1 and #2, the ability of ultrasound biomarkers to discriminate binary outcomes (malignant/benign and responsive/unresponsive to treatment) will be analyzed using logistic regression. The area under the receiver operating characteristic curve (AUC) will be quantified, with separate models fit for each of the eight ultrasound biomarkers. Because most ultrasound biomarkers are continuous measures, the best-balanced cutpoints optimizing sensitivity and specificity will be calculated, using Youden's Index. Outcome discrimination by dual biomarkers will be analyzed in 28 separate models with combinations of any two ultrasound biomarkers. The combined benefit of ultrasound and mammography will be analyzed in 32 models, by adding a single mammography metric (lesion size, density, shape, or margins) to each of the eight ultrasound biomarker models. In Aim #2, the relationship between biomarker values and tumor size, biomarker values and change in tumor size, and change in biomarker values and change in tumor size will be analyzed by linear regression. These correlations will be analyzed in separate models for each of the eight ultrasound biomarkers, in models of dual ultrasound biomarkers, and in models combining mammography metrics with ultrasound biomarkers.

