6.2 Sample Size and Accrual

A total of 80 participants will be recruited for this study. The study will be conducted in 40 women with diagnosed BIRADS-4 or -5 masses and in 40 women with malignant masses undergoing neoadjuvant chemotherapy.

We project 12 of the 40 women in our study will have malignant cancer, and 12 of 40 will have masses that do not respond to NAC. Given this, we expect 80% power to detect a minimum AUC of 0.70 (95% CI: 0.51 – 0.89). This is consistent with the diagnostic accuracy previously reported for malignancy detection by ultrasound biomarkers, which have ranged from AUC values of 0.67 to 0.99.^{5,10}

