Positive response to NAC will be dichotomized into a yes/no response, and the predictive ability of serial change in ultrasound metrics from baseline to end of

chemotherapy type will be analyzed by constructing separate ROC curves for combinations of any 2 ultrasound metrics.

6.3.2.8 What is the combined performance of ultrasound metrics and mammography for predicting a reduction in tumor size following NAC?

Reduction in tumor size will be dichotomized into a yes/no response. We will select ultrasound metrics with an AUC exceeding 0.75 in 6.3.2.1, 6.3.2.3, 6.3.2.5, and 6.3.2.7, and their combined diagnostic accuracy with mammography measures (mass size, density, shape, and margins) will be analyzed in separate ROC curves.

6.3.2.9 What are the sensitivity, specificity and PPV of ultrasound outcome metrics for identifying masses that positively respond to treatment?

Best-balanced cutpoints from the highest performing ultrasound metrics in 6.3.2.1 and 6.3.2.3 will be derived from ROC curves, using Youden's Index. These cutpoints will be used to analyze the PPV of positive response to NAC (dichotomized as a yes/no variable).

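### Section 6.1 plans 32 mammography models for all eight ultrasound metrics, but four other sections fit them only when the observed AUC exceeds 0.75, a bar that a single metric with true AUC 0.70 misses about 70% of the time

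*Combined protocol and SAP*

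**What the plan says.** Section 6.1 describes the mammography analysis without any condition: "The combined benefit of ultrasound and mammography will be analyzed in 32 models, by adding a single mammography metric", where that measure is lesion size, density, shape or margins, and it is added "to each of the eight ultrasound biomarker models". The count of 32 is 8 × 4, so every metric is included.

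The aim-specific sections set a condition on the same analysis:

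- Section 2.1.3 (Aim 1 objective): "For ultrasound outcome metrics (singly or combined) with AUC exceeding 0.75 in 2.1.1 and 2.1.2". Both single metrics and pairs are admitted, and the question is whether adding mammography improves on the ultrasound model alone.
- Section 6.3.1.3 (Aim 1 analysis): "We will select ultrasound metrics with an AUC exceeding 0.75", followed by a reference to C.1.a-b. The numbering C.1.a-b does not exist in this document; section 2.1.3 shows that the single-metric and two-metric analyses are meant.
- Sections 2.2.8 and 6.3.2.8 (Aim 2): the latter reads "We will select ultrasound metrics with an AUC exceeding 0.75 in 6.3.2.1, 6.3.2.3, 6.3.2.5, and 6.3.2.7". These four analyses cover single metrics and pairs, at baseline and as serial change.

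Section 6.2 projects 12 malignant lesions among 40 women in Aim 1 and 12 non-responding masses among 40 in Aim 2. It states that "we expect 80% power to detect a minimum AUC of 0.70", with a 95% CI of 0.51 to 0.89.

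**The concern.** An analyst cannot follow both rules. Under section 6.1 the set of mammography models is fixed in advance. Under the other four sections it depends on the data, and the single-metric part could be anything from no models to all 32.

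The threshold is also applied to a noisy estimate. The observed AUC comes from 40 women with about 12 in the smaller outcome group, and the same women then supply the combined models. Two consequences follow. A metric at the minimum AUC that section 6.2 says the study can detect will usually not get its single-metric mammography models. A metric of that strength that does get them enters the comparison with an AUC that is too high, because it was selected for being high. Correcting the surviving AUCs for optimism afterwards does not bring back the models that were never fitted.

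**Working it through.** **Inputs.** Minimum AUC 0.70, 95% CI 0.51 to 0.89, and outcome split 12 to 28 (section 6.2). Threshold 0.75 (sections 2.1.3, 2.2.8, 6.3.1.3 and 6.3.2.8). Eight metrics, 28 pairs and four mammography measures (section 6.1).

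**Step 1: reproduce the plan's CI.** The Hanley-McNeil variance with m = 12 cases and n = 28 non-cases is

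Var = [A(1−A) + (m−1)(Q1−A²) + (n−1)(Q2−A²)] / (mn), with Q1 = A/(2−A) and Q2 = 2A²/(1+A).

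At A = 0.70, Q1 = 0.5385, Q2 = 0.5765 and A² = 0.49. The variance is [0.21 + 11 × 0.0485 + 27 × 0.0865] / 336 = 3.078 / 336 = 0.00916, so SE = 0.0957. The interval 0.70 ± 1.96 × 0.0957 is 0.512 to 0.888, which matches the stated 0.51 to 0.89. What follows rests on this SE and not on the 80% power figure.

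**Step 2: chance that a single metric misses the threshold.** P(observed AUC ≤ 0.75 | true AUC 0.70) = Φ(0.05 / SE).

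- Hanley-McNeil SE 0.0957: Φ(0.522) = 0.699.
- SE implied by the stated CI, 0.19 / 1.96 = 0.0969: Φ(0.516) = 0.697.
- Obuchowski binormal SE 0.0950: 0.701.
- Binormal simulation, 200,000 trials: 0.701.

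The result is 0.68 to 0.72 for binormal data with unequal variances, and 0.67 to 0.73 for 8 to 20 cases among 40. In Aim 2, if the 28 responders are taken as the positive class, the Hanley-McNeil SE is 0.0857 and the result is Φ(0.583) = 0.720.

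**Step 3: behaviour across true AUCs.** Binormal simulation with equal variances, 12 to 28, one metric judged singly:

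| True AUC | Passes 0.75 |
|---|---|
| 0.50 | 0.5% |
| 0.60 | 6% |
| 0.65 | 14% |
| 0.70 | 30% |
| 0.75 | about 52% |
| 0.80 | 75% |
| 0.85 | 92% |
| 0.90 | 99% |

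At true AUC 0.70, the mean observed AUC among trials that pass is 0.80, about 0.10 too high.

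**Step 4: number of models.** Section 6.1 fixes 8 × 4 = 32. Under the threshold, Aim 1 can have from 0 to 32 single-metric models, and up to (8 + 28) × 4 = 144 once pairs are counted. In Aim 2, baseline and serial change together allow up to 2 × 144 = 288.

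**Step 5: return through pairs.** Three illustrative simulations gave the metric of interest a true AUC of 0.70. The other seven were set either to no signal and independent, or to AUC 0.70 with correlation 0.5 or 0.8, and pairs were scored by an in-sample linear discriminant. Of the metrics that missed singly, 46 to 71% came back in at least one passing pair, so 21 to 37% were lost by both routes. The documents do not give these correlations or AUCs; they are assumptions.

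**The case against.** The study calls itself exploratory. A threshold written down in advance is a legitimate way to limit the number of models, and one set above the smallest detectable AUC is not in itself an error: section 6.2 gives 0.70 as a minimum, not as the value the metrics are expected to reach. Section 6.2 also cites earlier AUCs of 0.67 to 0.99, and in the upper part of that range the threshold seldom fails. This stands as a defence of screening in general. It does not reconcile the four sections with section 6.1, which already commits to all 32 models.

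Three stronger readings are tempting, and the documents do not support them.

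- A reader might infer that a metric with true AUC 0.70 gets no mammography analysis at all 70% of the time. The rule also admits pairs, and in Aim 2 serial change, so the 70% applies only to a metric judged singly.
- A reader might infer that the threshold selects largely on chance. Pass rates rise from 0.5% at true AUC 0.50 to 99% at 0.90. It separates weak metrics from strong ones and is unreliable only in the region around 0.75.
- A reader might object that a stand-alone AUC does not show what ultrasound adds to mammography. Section 2.1.3 asks the reverse, namely what mammography adds to ultrasound, and no mammography-alone model is planned. Removing the threshold would not answer the other question.

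**Conclusion.** The contradiction is plain from the text: section 6.1 and the four threshold sections describe the same analysis and agree only if all eight metrics exceed 0.75. The threshold has a measurable cost near the plan's own minimum AUC. A single metric with true AUC 0.70 misses it about 70% of the time (0.67 to 0.73 over 8 to 20 cases of 40), and when it passes, its observed AUC averages about 0.80. These figures assume the projected 12 to 28 split and roughly binormal data, and they use a standard error that reproduces the stated CI. The share lost once pairs are allowed is smaller, but it depends on correlations that the documents do not give. The point deserves correction before analysis because it decides which models are fitted and reported; it does not undermine the ultrasound-only analyses.

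**What to change.** Remove the AUC > 0.75 condition for single metrics in sections 2.1.3, 2.2.8, 6.3.1.3 and 6.3.2.8. Fit and report all 32 models of section 6.1 in each aim, comparing each with the corresponding ultrasound-only model, as section 2.1.3 asks. In Aim 2, fit the 32 for the baseline metrics and state whether serial-change metrics are also included. State whether pair-plus-mammography models are still planned, since the 32 do not cover them. If they are kept, label them as exploratory and selected on the same data, and report how many were fitted. Replace the reference to C.1.a-b with the current section numbers.

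This changes wording only and needs no new patients, data or procedures. The cost is a longer results table and more in-sample comparisons with about 12 women in the smaller outcome group. Removing the condition ends selection among the single-metric models, but it does not by itself remove optimism in AUCs estimated on the data used to fit them.

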2.0 STUDY OBJECTIVES

The purpose of this study is to evaluate *in vivo* the diagnostic relevance of ultrasound-derived stiffness, elasticity, viscosity, and anisotropy metrics for breast lesion malignancy and response to treatment.

2.1 Aim #1: Quantify the ability of ultrasound-derived stiffness, elasticity, viscosity, and anisotropy to detect malignancy.

In vivo ARFI, VisR, and DDAI imaging will be performed in 40 women with a breast mass with a BIRADS breast assessment categories of -4a, 4b, 4c, or -5 rating after diagnostic workup. First, the transducer will be placed lightly above the suspicious mass, just to the point of skin contact, to avoid pre-compression during imaging.¹⁵ The suspicious mass will be positioned at 10 to 40 mm in axial depth, with standoff used if needed to achieve the desired axial position. Second, the position of the transducer will be rotated through 90° in steps of 30° to identify the transducer position yielding maximum ARFI peak displacement in the mass. The transducer will be stabilized in this position, with light skin contact, by the sonographer or by using a stereotactic clamp. Third, ARFI and VisR data will be acquired in immediate succession. Fourth, the transducer will be rotated 90°, re-stabilized by the sonographer or by using the stereotactic clamp, and ARFI and VisR data will be acquired in the new transducer position to enable DDAI analysis. Finally, the evaluated mass will undergo clinically indicated biopsy with histological evaluation to determine if it is benign or malignant.

The ultrasound data will be processed to calculate the following outcome metrics: peak displacement (PD), displacement at a given time (TD) for ARFI; τ , relative elasticity (RE), relative viscosity (RV), and tissue mass (TM) for VisR; ratio of ARFI PD and ratio of VisR RE values at 90° versus 0° transducer orientations for DDAI. These eight outcome metrics, alone and in combinations, will be statistically correlated with biopsy finding of malignant or benign.

2.1.1 Determine which of the 8 ultrasound metrics best detects malignancy.

We will statistically evaluate all eight ultrasound outcome metrics independently to determine which metric best detects malignant finding.

2.1.2 Determine the combined diagnostic accuracy of any 2 ultrasound metrics.

We will systematically combine all possible groupings of two ultrasound outcome metrics. We will then determine which grouping of metrics best detects malignant finding.

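### Best metric, best pair and Youden cutpoints are chosen and evaluated in the same 40 women with no internal validation, so their reported accuracy is biased upward

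*Combined protocol and SAP*

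**What the plan says.** Section 2.1.1 states "We will statistically evaluate all eight ultrasound outcome metrics independently to determine which metric best detects malignant finding". Section 2.1.2 does the same for pairs: "We will then determine which grouping of metrics best detects malignant finding". Section 6.1 fixes the number of pair models: "Outcome discrimination by dual biomarkers will be analyzed in 28 separate models with combinations of any two ultrasound biomarkers".

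Cutpoints follow from the selected metrics. Section 2.1.4 reads "Best-balanced cutpoints from the highest performing ultrasound metrics in 2.1.1 will be derived, and PPV will be calculated", and 6.3.1.4 reads "Best-balanced cutpoints from the highest performing ultrasound metrics in 6.3.1.1 will be derived from ROC curves", using Youden's Index. In Aim 1 this covers single metrics only. In Aim 2, section 6.3.2.9 takes cutpoints from the baseline single metrics (6.3.2.1) and the baseline pairs (6.3.2.3). Section 2.2.9 names 2.2.1 and 2.2.4 instead.

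Models with an AUC above 0.75 go on to be combined with mammography (6.3.1.3, 6.3.2.8). Section 6.1 adds mammography to the single-metric models regardless of AUC: "by adding a single mammography metric (lesion size, density, shape, or margins) to each of the eight ultrasound biomarker models".

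Section 6.2 allots all 80 women to the two aims, 40 each, and projects the split: "We project 12 of the 40 women in our study will have malignant cancer, and 12 of 40 will have masses" (the second 12 being non-responders). It adds "we expect 80% power to detect a minimum AUC of 0.70". Neither section 6 nor the rest of the document mentions a hold-out, cross-validation, bootstrap, optimism correction or validation cohort.

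**The concern.** Two sources of optimism are built in. First, the largest of 8 or 28 estimated AUCs is reported as the AUC of the winner, and the maximum of noisy estimates overstates the true value of whatever was picked. Second, the Youden cutpoint maximises sensitivity plus specificity in the same women in whom sensitivity, specificity and PPV are then read off. With 12 women in the smaller class, both effects can be large. It is the performance at the cutpoint that is biased upward, not the cutpoint's numerical location.

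Which metric, which pair, which cutpoint and what PPV are named objectives (2.1.1–2.1.4 and 2.2.1–2.2.9), so the affected numbers are the study's main product. A reader could take a PPV near 0.5 as evidence of diagnostic value when noise alone produces it.

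**Working it through.** **Inputs from the documents.** 40 women per aim, 12/28 split, design AUC 0.70 (6.2); 8 single metrics and C(8,2) = 28 pairs, so 36 models (6.1); screen at AUC 0.75 (6.3.1.3, 6.3.2.8). The documents give neither the correlation between metrics nor their true AUCs. Both are assumed and varied.

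**The plan's own figure.** Hanley–McNeil at AUC 0.70 with 12 and 28: Q1 = 0.70/1.30 = 0.538; Q2 = 2(0.49)/1.70 = 0.576. Variance = [0.21 + 11(0.538 − 0.49) + 27(0.576 − 0.49)]/(12 × 28) = 0.00916 (unrounded Q1 and Q2), so SE = 0.0957. The interval is 0.70 ± 1.96 × 0.0957 = 0.51 to 0.89, as stated. The 80% power is not reproduced at alpha 0.05 against a null AUC of 0.50: the null SE is √(41/(12 × 12 × 28)) = 0.101, which gives 51% two-sided and 64% one-sided. That is a separate matter, and nothing below rests on it.

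**Simulation.** Metrics are normal and equicorrelated, shifted by d = √2·Φ⁻¹(AUC) in the positive class. Single AUCs are taken in whichever direction the data favour, pairs are fitted by logistic regression, and the best is chosen by apparent AUC. The cutpoint c maximises J = sensitivity + specificity − 1. PPV = se·π/[se·π + (1 − sp)(1 − π)], with π = 12/40 = 0.30 in Aim 1 and 28/40 = 0.70 in Aim 2. Truth is computed analytically for the selected rule; for a single metric, se = 1 − Φ(c − d) and sp = Φ(c). For a noise metric se = 1 − sp, so the true PPV equals π. Runs used 2,000–4,000 trials per scenario. Entries are trial averages, so the PPV is not exactly the PPV at the mean sensitivity and specificity.

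Best single metric, 12/28 split, in-sample value vs truth:

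| True AUCs (correlation) | AUC | Sensitivity | PPV |
|---|---|---|---|
| All 0.50 (0–0.8) | 0.64–0.68 vs 0.50 | not tabulated | 0.49–0.52 vs 0.30 |
| One 0.80, seven noise (0.3) | 0.80–0.81 vs 0.77–0.78 | 0.81 vs 0.66–0.68 | 0.63 vs 0.52–0.53 |
| All 0.70 (0.3–0.8) | 0.76–0.81 vs 0.70 | not tabulated | 0.58–0.62 vs 0.44–0.46 |
| Spread 0.50–0.75 (0.3–0.8) | 0.77–0.79 vs 0.71 | 0.79–0.80 vs 0.60–0.63 | 0.59–0.61 vs 0.46–0.47 |
| One 0.90, seven noise | 0.90 vs 0.90 | 0.88 vs 0.78 | 0.73–0.74 vs 0.66–0.68 |
| One pre-chosen metric at 0.80, no selection | 0.80 vs 0.80 | 0.81 vs 0.70 | 0.62–0.63 vs 0.54–0.55 |

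The last row separates the two mechanisms. Without any choice of metric the AUC is unbiased, yet sensitivity and PPV at the in-sample cutpoint are still inflated.

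**Pairs.** The best pair reads 0.73 when all metrics are noise. With one metric at 0.80 and correlation 0.3 it reads 0.87 against a true 0.78 (gap 0.05–0.10 over correlations 0–0.8).

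**The 0.75 screen.** With all metrics noise, at least one of the 36 models passes in 31–33% of trials. With all metrics at 0.70, a single metric passes in 57–82%.

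**Aim 2, all noise, 28 responders.** PPV reads 0.85–0.87 for the best single metric and 0.89 for the best pair, against 0.70. Sections 6.3.2.1, 6.3.2.3, 6.3.2.5 and 6.3.2.7 feed the screen with 8 + 28 + 8 + 28 = 72 models. At least one passes in 50–56% of trials, under assumed correlations between baseline and change values.

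**Does correction work?** Bias of apparent / nested cross-validation / bootstrap, best single metric, selection and cutpoint repeated inside (1,000 trials, 5 × 4-fold nested CV, 60 bootstraps):

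| Scenario | AUC | PPV | PPV RMSE |
|---|---|---|---|
| All noise | +0.17 / −0.01 / +0.05 | +0.21 / 0.00 / +0.07 | 0.235 / 0.085 / 0.133 |
| One at 0.80 | +0.035 / −0.016 / −0.014 | +0.11 / −0.02 / +0.02 | 0.148 / 0.128 / 0.113 |
| Spread 0.50–0.75 (0.6) | +0.07 / −0.01 / +0.01 | +0.14 / −0.02 / +0.04 | 0.171 / 0.108 / 0.114 |

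For the best pair (300 trials), AUC bias was +0.23 / +0.01 / +0.09 with all noise, +0.08 / −0.02 / 0.00 with one metric at 0.80, and +0.12 / −0.02 / +0.03 with the spread.

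**The case against.** - **The study is exploratory.** Section 1.4 says so, and biopsy and chemotherapy are unaffected. This stands as a limit on the consequence. It does not tell a reader that the PPV is in-sample, and the same section sets out to show that the methods detect malignancy reliably.
- **The largest numbers assume pure noise.** Section 6.2 cites prior AUCs of 0.67 to 0.99. If one metric truly reaches 0.90, AUC bias vanishes and PPV bias shrinks to about 0.05–0.08. That is right, and the size depends on where the new metrics fall. Sensitivity is still overstated by 0.10 in that case.
- **More than the winner may be reported.** Section 6.1 does not confine cutpoints to the best metrics, and 6.3.1.4 speaks of metrics in the plural. Reporting all of them would weaken the selection effect but not the cutpoint effect.
- **The 0.75 screen is minor.** Agreed: it only triggers further ROC curves with mammography.
- **Correction is noisier and only partly tested.** With one dominant metric at 0.80, the apparent AUC has the lowest RMSE (0.097, against 0.121 for nested CV and 0.107 for bootstrap). Corrected sensitivity, specificity and PPV for pairs, and corrected mammography increments, were not simulated. This stands, and it is why corrected values should accompany the apparent ones rather than replace them.

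**Conclusion.** The concern holds and should be fixed. Followed as written, the plan reports apparent accuracy after selection. Sensitivity, specificity and PPV at the selected cutpoint are too high in every scenario tried. Single-metric PPV is overstated by roughly 0.05–0.08 with one metric at 0.90, by about 0.10 with one at 0.80, and by about 0.2 when all metrics are noise. The AUC of the best single metric is nearly right if one metric dominates and is clearly inflated if several perform alike; the best-pair AUC is inflated in each scenario for which it is given.

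Confidence is high for the direction and moderate for the size. The size rests on normal metrics, equicorrelation, the projected 12/28 split and assumed true AUCs. The scope of Aim 2 cutpoints follows 6.3.2.9, which 2.2.9 contradicts.

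**What to change.** In sections 6.1 and 6.3:

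1. Report AUCs with confidence intervals for all 8 metrics and 28 pairs, labelled as apparent.
2. For each selected metric or pair, and for any mammography increment, also report AUC, sensitivity, specificity and PPV corrected by resampling that repeats selection, fitting and cutpoint choice in every resample. Nested cross-validation or bootstrap optimism correction will do; if the bootstrap is used, state its residual upward bias.
3. Call the 0.75 screen exploratory and do not use corrected values as a hard gate. Nested-CV AUC has an SD of 0.10–0.13 and falls below 0.75 in about 40% of trials even with one metric truly at 0.80.
4. State that any cutpoint derived on all 40 women needs external validation.
5. Reconcile two Aim 2 points so that the resampled procedure is defined. The cutpoint source differs between 2.2.9 and 6.3.2.9, and 2.2.4 is a correlation with tumor size that yields no ROC curve. The change window is 0–6 weeks in 6.3.2.5 but runs to the end of the chemotherapy type in 2.2.5 and 6.3.2.7; the imaging schedule in 4.2.2 fixes no scan at six weeks.

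The cost is wording and a short script, with no extra patients or data. The corrected figures will be lower and less precise, and nested CV is noisier than the apparent value for specificity.
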